The items being used to measure beliefs have Likert-type response scales. Conceptually, the response categories for a Likert response scale represent an underlying belief continuum. For warning statements with multiple corresponding items, we will assess whether to scale the items, using the following protocol:

- 1) Run a test of internal consistency reliability using Cronbach's alpha (Cronbach, 1951) on all of the items in a domain. If the test indicates "modest" reliability of $\alpha \geq 0.70$ (Nunnally & Bernstein, 1994), scale the items.

- 2) If $\alpha < 0.70$, but all item-total correlations (i.e. the correlation between the item score and the overall scale score) are ≥ 0.4 , scale the items (Item-total correlations of between 0.30—0.40 and greater have been suggested as sufficiently discriminating (Nunnally & Bernstein, 1994; Traub, 1994; Leong & Austin, eds., 2006)
- 3) If criteria 1 and 2 are not met, determine whether the scale alpha would increase to ≥ 0.70 if any items were deleted from the scale (i.e. using Stata’s “alpha” command with “item” option specified). If the alpha value threshold would be met by dropping an item or items:
 - a. Drop those items to form a scale with $\alpha \geq 0.70$
 - b. Also run analyses of each item individually
- 4) Otherwise, run analyses of each item individually

We are measuring beliefs at each study session. The above procedure to inform the scaling of the belief items will be made on the beliefs assessed at Session 1 (baseline) and then applied to the beliefs measured at the remaining sessions. We do not expect the measurement structure of beliefs to change over a longitudinal sample over a relatively short period of time. Assuming attrition across study sessions, basing the measurement structure on the Session 1 sample utilizes the largest available sample.

To determine the GHW’s immediate impact on targeted beliefs, we will examine the extent to which pre-post differences in beliefs vary between those exposed to GHW (treatment) and SG warnings (control). The general form of this analysis approach is as follows:

$$(\text{Belief}^T_{S2} - \text{Belief}^T_{S1}) - (\text{Belief}^C_{S2} - \text{Belief}^C_{S1})$$

where Belief represents the average value (for continuous variables) or probability of being in a higher response category (for ordinally-treated variables), among those in a Treatment (*T*) or Control (*C*) group, at Session 2 (*S2*) or Session 1 (*S1*).

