For each treatment versus control comparison, will test hypotheses of the following general form:

- H_0 : Average pre-post difference in belief score for those in the treatment condition = average pre-post difference in belief score in the control condition
- H_a : Average pre-post difference in belief score for those in the treatment condition \neq average pre-post difference in belief score in the control condition

To test the hypotheses for Phase 2 analyses, for each outcome we will estimate a regression model of the following general form:

$$\text{Belief} = f(\text{Condition}, \text{Session}, \text{Condition}*\text{Session}, \text{Age}, \text{Smoking Status})$$

where Belief is a measure of agreement with a statement (or set of statements) about the health effects of cigarette smoking, Condition is a dichotomous indicator for a treatment versus control condition, Session is a dichotomous indicator for Session 2 versus Session 1, Condition*Session is the interaction between study condition and study session, Age is a categorical variable for age group (i.e. youth aged 13-17; young adults aged 18-24; and adults aged 25+), and Smoking Status is an indicator for current smoking versus not current smoking (in the adult and young adult samples non-current smokers are never smokers and in the youth sample non-current smokers are those youth susceptible to smoking). These models will include covariates for age and smoking status group to account for potential associations between age, smoking status and outcomes of interest. The key variable of interest in these models is the interaction term, Condition*Session. The coefficient on Condition*Session indicates whether the pre-post change in belief was greater among respondents exposed to a GHW as compared to those exposed to a SG warning. This general model will be repeated for each of 16 treatment versus control group comparisons.

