For those statements which have multiple corresponding belief items that can be scaled into a single continuous variable, we will test these hypotheses using linear regression. For statements with single ordinal Likert-type belief items or for which multiple items are not scalable, we are testing hypotheses of the form that treatment (being exposed to GHW) is associated with a greater pre-post change in level of the ordinal dependent variable than being in the control group (being exposed to an SG warning). Thus, for these items we will use ordinal logistic regression. All regressions, both logistic and linear will be estimated in Stata version 14.1 and will be estimated using Stata's robust standard errors.

In the cases where the dependent variable is continuous and a linear regression model is estimated, the interaction term (Session*Condition) represents the difference in difference of the means or treatment effect. However, in a non-linear model, such as when the dependent variable is ordered and we estimate an ordinal regression model, the coefficient of the interaction term is not a direct measure of the treatment effect due to the non-linear model. As noted in Puhani (2012), in a non-linear model with a strictly monotonic transformation function of a linear index, the sign of the coefficient of the interaction term is equal to the sign of the treatment effect. Testing the significance of the interaction term in the non-linear model is best done via bootstrapping (Puhani, 2012).

As a supplement to the analyses above, we will conduct parallel analyses stratified by age group (i.e. youth aged 13-17; young adults aged 18-24; and adults aged 25+) and smoking status (current smoker versus non-smoker), to examine potential effects within each age and smoking status group. Of note is that this study is not sufficiently powered to detect within-age or

smoking status group differences, and so results from the stratified analyses should be interpreted with caution (i.e., a non-significant finding within an age or smoking status group may reflect lack of statistical power).

A total of 16 statistical tests will be conducted in Phase 2 (not including supplemental age-stratified analyses). To account for the possibility of falsely detecting a significant result (i.e. Type 1 error) arising from multiple statistical tests, we will control for the False Discovery Rate (FDR) using the Benjamini-Hochberg procedure (assuming a two-tailed test and FDR of 0.05).

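### For ordinal belief items, Phase 2 never estimates the probability effect it defines, and its inference rule neither clusters on the respondent nor says which p-value enters Benjamini-Hochberg

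*SAP*

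**What the plan says.** All of this is in SAP section 4.2.

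- **Effect defined.** The general form of the Phase 2 analysis is the treatment change minus the control change. For ordinal items the quantity in each of the four cells is a "probability of being in a higher response category (for ordinally-treated variables"). No cut-point is named.
- **Parameter estimated.** "The key variable of interest in these models is the interaction term, Condition*Session". The plan says its coefficient "indicates whether the pre-post change in belief was greater among respondents exposed to a GHW as compared to those exposed to a SG warning".
- **Caveat.** For ordinal models the plan adds that "the coefficient of the interaction term is not a direct measure of the treatment effect due to the non-linear model", and relies on the result that "the sign of the coefficient of the interaction term is equal to the sign of the treatment effect".
- **Inference.** "All regressions, both logistic and linear will be estimated in Stata version 14.1" and "will be estimated using Stata's robust standard errors". In the next paragraph, on non-linear models: "Testing the significance of the interaction term in the non-linear model is best done via bootstrapping".
- **Multiplicity.** There are 16 two-sided Phase 2 tests, under Benjamini-Hochberg at an FDR of 0.05.
- **Scope.** In Table 5, conditions 1 to 5 and 8 have a single item and are always ordinal. The other ten are ordinal if their items do not scale. Model 2 (Session 3 versus Session 1) takes over the same models, tests and interpretation.

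**The concern.** Two things are left open.

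First, the plan defines an effect for ordinal items and then provides no route to it. Nothing asks for predicted probabilities, a marginal effect or an interval for the defined contrast. A 5-level item has four cut-points, each with its own probability contrast. An ordinal item would therefore yield a test and a log-odds coefficient, but no effect size on the defined scale. Scaled items, by contrast, would be reported in belief points.

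Second, the source of the p-value is not fixed. The robust standard-error rule does not mention the respondent as a cluster, although the model stacks a baseline row and a follow-up row for each person followed up. The bootstrap remark comes without a commitment, a resampling unit or a number of replicates. Ordinary robust standard errors treat the two rows as independent, and so would a bootstrap that resamples rows. When answers are positively correlated within person, both overstate the uncertainty of a within-person change. The harm would be missed effects, because the test becomes too conservative.

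**Working it through.** **1. Reproducing a figure from the plan.** Inputs from SAP section 3: difference 0.3, SD 1, two-sided tests, 50% retention. With within-person correlation r, the SD of a change score is sqrt(2(1 − r)). For the Table 3 row with 880 control, 250 treated and r = 0.4:

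- SD = sqrt(1.2) = 1.095
- SE = 1.095 × sqrt(1/880 + 1/250) = 0.0785
- power = Φ(0.3/0.0785 − 1.96) = 0.969

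Table 3 gives 0.98 unadjusted. The gap is within the Monte Carlo error of 100 simulations (standard error about 0.017), so Table 3 is consistent with a respondent-level change-score analysis.

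**2. The same setting with rows treated as independent.** The planned 2,080 and 480 become 1,040 and 240 at 50% retention, and sqrt(1/1040 + 1/240) = 0.0716. The calculation assumes respondents with both rows and no covariates.

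- Correct SE at r = 0.4: 1.095 × 0.0716 = 0.0784
- Unclustered SE: sqrt(2) × 0.0716 = 0.1013
- Ratio: 1/sqrt(1 − 0.4) = 1.29
- Size: 2 × (1 − Φ(1.96 × 1.29)) = 0.011
- Power: Φ((0.3 − 1.96 × 0.1013)/0.0784) = 0.90, against 0.97 with the correct SE

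| r | SE ratio | size, unclustered | power, unclustered | power, respondent as unit |
|---|---|---|---|---|
| 0 | 1.00 | 0.050 | 0.84 | 0.84 |
| 0.2 | 1.12 | 0.028 | 0.87 | 0.91 |
| 0.4 | 1.29 | 0.011 | 0.90 | 0.97 |
| 0.6 | 1.58 | 0.002 | 0.94 | 0.997 |

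**3. Does this carry over to a logistic interaction?** A simulation used 1,040 and 240 respondents, one binary cut, an assumed latent correlation of 0.6 and 2,000 trials per setting. With no effect, the unclustered test rejected in 0.6% to 2.5% of trials, and the respondent-level test in 4.1% to 5.4%. With an assumed interaction of 0.4, the unclustered and respondent-level powers were 0.51 and 0.73 at a baseline probability of 0.50, 0.25 and 0.42 at 0.80, and 0.12 and 0.23 at 0.90. The direction is the same.

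**4. What the coefficient says about effect size.** Take equal baselines and an assumed interaction of 0.4. The probability contrast is F(logit p + 0.4) − p, where F is the inverse logit and p is the Session 2 probability without the interaction.

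- p = 0.50: 0.099
- p = 0.70: 0.077
- p = 0.90: 0.031

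Within one item with assumed thresholds at −4, −3, −2 and −0.5 and a session shift of 0.2, the four cut-points give 0.005, 0.013, 0.031 and 0.082. One coefficient therefore fixes no single probability effect.

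**5. Two candidate effect sizes are not the same.** Suppose treatment moves from 0.90 to 0.94 and control from 0.80 to 0.86.

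- Four-cell contrast: 0.04 − 0.06 = −0.02
- Logit interaction: 0.554 − 0.429 = +0.125
- Follow-up contrast with the interaction set to zero: 0.94 − F(2.197 + 0.429) = 0.94 − 0.9325 = about +0.007

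The three coincide in sign when baselines are equal, but need not when they differ.

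**6. Scope.** Six comparisons are always ordinal. If no item set scaled, all 16 would be, with 1+1+1+1+1+2+2+1+5+3+3+3+3+2+3+2 = 34 item-level models.

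**The case against.** A reader might infer that Phase 2 tests the wrong quantity for ordinal items. The documents do not support that. The plan says the coefficient is not a direct measure of the effect, not that it is unrelated to it, and gives the sign result as its reason for testing it. It also restates the hypothesis for ordinal items as a change in the level of the ordinal outcome. Beliefs are measured before randomisation, so expected baselines are equal, and a zero interaction and a zero probability contrast then coincide. In the simulation the two signs disagreed in 0.1% to 9% of trials, mostly where the effect was null or small. This part of the objection stands, apart from chance baseline imbalance (step 5).

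A reader might also infer that the plan mandates two contradictory methods. It does not. The bootstrap sentence is a statement of good practice about one test and can be read as qualifying the general rule. What remains is that nothing commits to it, and nothing says which p-value is ranked.

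The plan does not rule out clustering either. If its robust standard errors were clustered on the respondent, they and a respondent-level bootstrap should agree closely at these sample sizes. The numbers in step 2 apply only if the rule is followed as written. Finally, mixing log-odds and belief points across outcomes is ordinary practice and no error in itself.

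**Conclusion.** The point holds in limited form. For ordinal items the defined probability contrast has no cut-point and no estimation step, so these comparisons have a largely defensible test but no effect size on the defined scale. The inference rule, read literally, ignores that a respondent supplies two rows, and the bootstrap remark does not repair this because it is neither committed to nor tied to the respondent.

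The first defect affects 6 to 16 of the 16 comparisons, in Models 1 and 2. The second costs, at correlation 0.4 in the plan's linear setting, a standard error inflated about 1.29 times and power of about 0.90 instead of 0.97. It makes findings harder to reach and does not inflate false positives. The plan fixes neither the within-person correlation (Table 3 spans 0 to 0.8) nor any baseline distribution of beliefs. The logistic and probability figures therefore rest on assumed values and show direction and rough scale only.

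**What to change.** 1. **Inference.** Replace the plain robust standard-error commitment with one method for the interaction that takes the respondent as the unit. Either a bootstrap that resamples respondents with both their rows (seed and number of replicates stated) or respondent-clustered robust standard errors would do. State that this interaction p-value enters Benjamini-Hochberg. The robust standard-error sentence also covers the linear models for scaled items, so the new wording should too.
2. **Effect size.** For each ordinal model, also report one named effect from the model predictions with a 95% confidence interval. It can be the four-cell contrast at a stated cut-point (or on the mean score), or the follow-up contrast with the interaction set to zero. Reword the definition in section 4.2 to match the choice, since the two differ when baselines differ.
3. **Optional.** A linear model of the 1 to 5 score for the six single items would give a common unit across warnings. Label it descriptive and keep it outside the multiplicity family.

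The cost is SAP wording and short post-estimation code for Models 1 and 2. No new data are needed.

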4.3. Phase 3: Warning Label Recall

For the Phase 3 analysis, we will conduct comparisons of the proportion of respondents accurately recalling (at Session 3) the warning that they were exposed to at Sessions 1 and 2. We assess recall with the following item:

E1. You recently took a survey in which you were shown a cigarette pack and advertisement with a warning on it. Which label do you remember seeing?

1. LABEL 1
2. LABEL 2
3. LABEL 3
4. LABEL 4
5. None of these
6. I don't remember

Respondents in the control condition are shown each of the 4 SG labels; those in each treatment condition are shown the GHW that they were exposed to earlier along with 3 randomly selected additional GHWs. Thus, each respondent is shown one warning that they were exposed to earlier in the study, and 3 warnings (of the same type—GHW or SG) that they had not been exposed to. We will construct an indicator variable such that 1 = accurate recall of the warning to which the respondent was exposed and 0 = inaccurate or lack of recall (i.e., false recall of any of the 3 warnings not shown earlier in the study or a response of “None of these” or “I don't remember”).

For the Phase 3 analysis, we will test hypotheses of the following general form:

- H_0 : proportion (%) of those in the treatment condition accurately recalling the warning = proportion (%) of those in the control condition accurately recalling the warning
- H_a : proportion (%) of those in the treatment condition accurately recalling the warning \neq proportion (%) of those in the control condition accurately recalling the warning

Since the recall measure is dichotomous, we will test this hypothesis using logistic regression of the following form:

$$\text{Recall} = f(\text{Condition, Age, Smoking Status})$$

where Recall is a measure of accurate recall of the warning, Condition is a dichotomous indicator for a treatment versus control condition, Age is a categorical variable for age group (i.e. youth

aged 13-17; young adults aged 18-24; and adults aged 25+) and Smoking Status is an indicator for current smoking versus not current smoking (in the adult and young adult samples non-current smokers are never smokers and in the youth sample non-current smokers are those youth susceptible to smoking). These models will include covariates for age and smoking status group to account for potential associations between age, smoking status and outcomes of interest. The coefficient from the Condition variable indicates whether accurate warning recall was significantly greater among those exposed to a GHW as compared to those exposed to a SG warning. This general model will be repeated for each of 16 treatment versus control group comparisons. All regressions will be estimated in Stata version 14.1 and will be estimated using Stata's robust standard errors.

As a supplement to the analyses above, we will conduct parallel analyses stratified by age and smoking status group, to examine potential effects within each age and smoking status group. Of note is that this study is not sufficiently powered to detect within-age or smoking status-group differences, and so results from the stratified analyses should be interpreted with caution (i.e. a non-significant finding within an age or smoking status group may reflect lack of statistical power).

A total of 16 statistical tests will be conducted in Phase 3 (not including supplemental age-stratified analyses). To account for the possibility of falsely detecting a significant result (i.e. Type 1 error) arising from multiple statistical tests, we will control for the False Discovery Rate (FDR) using the Benjamini-Hochberg procedure (assuming a two-tailed test and FDR of 0.05) (Benjamini & Hochberg, 1995).

We do not anticipate substantial item non-response, nor do we expect that patterns of item non-response would vary significantly among study conditions. Thus, we will plan to use pairwise deletion to include all available data for each particular analysis. We will examine the data for issues of item non-response and differential item non-response and adjust our approach for handling missing data accordingly.

References

Benjamini, Y. & Hochberg Y. (1995). Controlling the false discovery rate: A practical and powerful approach to multiple testing. *J Roy Stat Soc. Series B*, 57(1), pp. 289–300.

Cronbach, L. J. (1951). Coefficient alpha and the internal structure of tests. *psychometrika*, 16(3), 297-334.

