Experimental Studies of Cigarette Graphic Warning Labels: Analysis Plan

1. Respondent Universe and Sampling Methods

The respondent universe for this study is (1) adolescent current cigarette smokers aged 13-17 years old; (2) adolescents who are susceptible to initiation of cigarette smoking aged 13-17 years old; (3) young adult current cigarette smokers aged 18 to 24 years old; (4) young adult nonsmokers aged 18 to 24 years old; (5) older adult current cigarette smokers aged 25 years old and older; and (6) older adult nonsmokers aged 25 years old and older.

Study participants will be recruited from a national online panel of adults managed by Lightspeed. The Lightspeed panel is a non-probability convenience sample recruited via social media, online recruitment (e.g. via banner placements), and affiliate corporate networks. For the current study, Lightspeed will recruit adult panelists and parents of potential youth respondents using information from panelist's user profiles related to study eligibility (i.e. age, smoking status, and whether or not the panelist has a child in the eligible age range).

Lightspeed panel members will receive an email inviting them to participate in the study. Adolescent children of adult panel participants will be invited to complete the survey through an email invitation to their parents asking for their consent to solicit their child's opinions. Panel members and children of panelists who choose to participate will complete the questionnaire. During the study recruitment, we will monitor the sample and can adjust recruitment targeting as needed to ensure the sociodemographic distribution is diverse in terms of age, gender, education, and ethnicity/race. We estimate a total of 9,760 respondents will complete the baseline data collection. We will administer two follow-up surveys of baseline survey participants, with estimated retention rates of between 50% - 100% for each follow-up session (Table 1).

[figure not shown]
Table 1. Estimated Sample Sizes, by Sample Group and Study Session

Age Group	Smoking Status	Session		
		1	2	3
Adolescent	Current Smoker	230	115 - 230	58 - 230
Adolescent	Susceptible to Smoking	2,070	1,035 - 2,070	518 - 2,070
Young Adult	Current Smoker	1,330	665 - 1,330	333 - 1,330
Young Adult	Nonsmoker	1,330	665 - 1,330	333 - 1,330
Older Adult	Current Smoker	2,400	1,200 - 2,400	600 - 2,400
Older Adult	Nonsmoker	2,400	1,200 - 2,400	600 - 2,400
Total		9,760	4,880 - 9,760	2,440 - 9,760

2. Study Protocol

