The study comprises three Sessions, outlined in Figure 1.

Figure 1. Study Protocol

In Session 1, participants will first complete a screening questionnaire through an email invitation. After screening for inclusion (see Study Screener), participants who qualify for the study will complete three consecutive components: (1) a baseline assessment of beliefs about the negative health consequences of cigarette smoking; (2) assignment to study condition and exposure to cigarette warning stimuli according to condition assignment; and (3) assessment of new information, self-reported learning, and other reactions to the stimuli (see Session 1 Survey Instrument). These three components are described below.

- *Component (1)*: First, participants will be asked questions about beliefs related to the health consequences of cigarette smoking.
- *Component (2)*: Following the baseline assessment of beliefs, participants will be randomized to one of 16 treatment conditions or a control condition with variation in exposure to cigarette warnings (Table 2 illustrates the targeted Session 1 sample size and allocation across experimental groups, within each age group and overall). Participants in each experimental condition will be exposed to one graphic health warning (GHW), with each condition corresponding to a unique warning from a set of 16. Participants in the control condition will be exposed to a random selection of one of four Surgeon General's (SG) warnings. Each stimuli exposure will include viewing of the warning in two formats: on a mock cigarette package depicted in a 3-dimensional, rotational model; and on a mock cigarette advertisement. In all analyses, stimuli exposure will be considered the joint exposure to both stimuli formats; stimuli format is not considered a study factor
- *Component (3)*: After viewing the warning stimuli in both package and advertisement formats, participants will complete a brief set of measures to assess (a) if the information presented in the warning was new; (b) self-reported learning from the warning; (c) if the warning was easy to understand; (d) if the warning was perceived to be a fact or an

opinion; (e) if the warning was informative; (f) if the warning grabbed their attention; and (g) if the warning made them think about the health risks of smoking.

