10	GHW	WARNING: Smoking causes COPD, a lung disease that can be fatal. [IMAGE 1: BRAIN]	113	131	236	480
11	GHW	WARNING: Smoking causes COPD, a lung disease that can be fatal. [IMAGE 2: MAN]	113	131	236	480
12	GHW	WARNING: Smoking reduces blood flow, which can cause erectile dysfunction.	113	131	236	480
13	GHW	WARNING: Smoking reduces blood flow to the limbs, which can require amputation.	113	131	236	480
14	GHW	WARNING: Smoking causes type 2 diabetes, which raises blood sugar.	113	131	236	480
15	GHW	WARNING: Smoking causes age-related macular degeneration, which can lead to blindness.	113	131	236	480
16	GHW	WARNING: Smoking causes cataracts, which can lead to blindness.	113	131	236	480
TOTAL			2,300	2,660	4,800	9,760

NOTE: SG = Surgeon General's Warning; GHW = Graphic Health Warning

3. Power Analysis

We conducted power calculations to confirm that the overall sample size (shown in Table 2) is sufficiently powered and to determine the optimal sample size and allocation of sample across study conditions. To control for Type 1 error taking into account multiple testing, power calculations were based on the false discovery rate (FDR) (Benjamini & Hochberg, 1995).

Assuming the tests are independent, the FDR is the expected proportion of significant results that are falsely declared as statistically significant. Controlling the FDR is controlling the expected proportion of falsely declared differences (i.e., false discoveries). Controlling the FDR is a more powerful method for dealing with multiple comparisons than other methods that control the family-wise error rate (Benjamini & Hochberg, 1995).

For the overall study sample size, we calculated power to detect a difference in the change in a tobacco-related belief from Session 1 to Session 2 between treatment and control groups (i.e., difference in difference) (Table 3 provides power estimates for Session 2 across various scenarios). RTI calculated power to detect a 0.3 difference on a 7-point scale (two-sided tests, assuming a standard deviation of 1) under different scenarios with variation in FDR, within-person correlation between Session 1 and 2, and sample allocation. RTI conservatively assumed 50% retention from Session 1 to Session 2. Power calculations were computed using 100 simulations for each sample allocation in SAS v9.4.

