Across various assumptions of within-person correlation and FDR, we found generally higher levels of power using an optimized sample allocation with between 1,760 and 2,400 participants assigned to the control condition at Session 1 (880-1,200 participants at Session 2, assuming 50% retention). Based on this analysis showing that higher power is achieved with an unbalanced allocation, FDA plans to allocate 2,080 to the control group and 480 to each treatment group at Session 1.

Table 3. Study Power by Sample Allocation at Session 2

Sample Allocation at Session 2		Within-person Correlation	FDR					Unadjusted Power
Control	Treatment		0.05	0.1	0.15	0.2	0.25	
287	287	0	0.60	0.71	0.83	0.89	0.91	0.68
880	250	0	0.80	0.89	0.94	0.95	0.97	0.85
1,200	230	0	0.77	0.87	0.90	0.94	0.95	0.81
1,520	210	0	0.88	0.92	0.94	0.96	0.98	0.88
1,840	190	0	0.72	0.84	0.88	0.92	0.93	0.78
287	287	0.2	0.64	0.77	0.83	0.89	0.90	0.73
880	250	0.2	0.95	0.95	0.97	0.99	0.99	0.96
1,200	230	0.2	0.89	0.94	0.95	0.98	1.00	0.91

1,520	210	0.2	0.87	0.92	0.94	0.96	0.98	0.89
1,840	190	0.2	0.85	0.88	0.94	0.94	0.99	0.87
287	287	0.4	0.85	0.91	0.96	0.98	0.99	0.89
880	250	0.4	0.97	0.98	0.99	0.99	1.00	0.98
1,200	230	0.4	0.97	1.00	1.00	1.00	1.00	0.97
1,520	210	0.4	0.95	0.97	0.97	0.97	0.98	0.95
1,840	190	0.4	0.91	0.94	0.97	0.97	0.97	0.91
287	287	0.6	0.97	0.98	0.98	1.00	1.00	0.98
880	250	0.6	1.00	1.00	1.00	1.00	1.00	1.00
1,200	230	0.6	1.00	1.00	1.00	1.00	1.00	1.00
1,520	210	0.6	1.00	1.00	1.00	1.00	1.00	1.00
1,840	190	0.6	1.00	1.00	1.00	1.00	1.00	1.00
287	287	0.8	1.00	1.00	1.00	1.00	1.00	1.00
880	250	0.8	1.00	1.00	1.00	1.00	1.00	1.00
1,200	230	0.8	1.00	1.00	1.00	1.00	1.00	1.00
1,520	210	0.8	1.00	1.00	1.00	1.00	1.00	1.00
1,840	190	0.8	1.00	1.00	1.00	1.00	1.00	1.00

Note: FDR = False Discovery Rate

4. Analysis

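### The recall item can show participants in the two COPD conditions a distractor with identical text, which makes recall harder for about one fifth of those two arms

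*SAP*

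**What the plan says.** SAP section 2 assigns each treatment participant to one graphic warning, "with each condition corresponding to a unique warning from a set of 16". In Table 2, condition 10 is "WARNING: Smoking causes COPD, a lung disease that can be fatal. [IMAGE 1: BRAIN"] and condition 11 is "WARNING: Smoking causes COPD, a lung disease that can be fatal. [IMAGE 2: MAN"]. The statement is the same word for word and only the image differs. No other statement is repeated among the 16 GHWs.

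Section 4.3 describes the Session 3 recall item, E1. In the treatment arms, "those in each treatment condition are shown the GHW that they were exposed to earlier along with 3 randomly selected additional GHWs". No label is excluded from the draw. In the control arm, "Respondents in the control condition are shown each of the 4 SG labels", and those four texts all differ. A correct choice scores 1. A score of 0 covers "false recall of any of the 3 warnings not shown earlier in the study", as well as answers that the participant saw none of the labels or cannot remember.

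The same logistic model (condition, age group, smoking status) is then fitted for each of the 16 contrasts with control. It has no term for the distractors shown, and no sensitivity analysis on them is planned.

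**The concern.** A recall item of this kind compares arms fairly only if the answer options are about equally hard to tell apart. A participant in condition 10 or 11 who remembers the statement perfectly, but not the picture, cannot separate the two COPD labels when both are on screen. The same quality of memory gives a correct answer in every other arm.

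Two of the 16 Phase 3 contrasts would then partly reflect the answer options rather than how memorable the warning is. The effect lowers recall in those arms, a larger sample does not remove it, and nothing in the planned analysis would reveal it. A real recall advantage for a COPD warning over the Surgeon General's (SG) warnings could be understated or missed.

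**Working it through.** The SAP gives no recall rate, no power for recall and no figure for distractor overlap, so there is nothing of its own to reproduce here. Its allocation does add up: 16 × 480 + 2,080 = 9,760.

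**Inputs from the SAP**
- 16 GHWs, so 15 possible distractors per treatment participant, of which 3 are drawn (sections 2 and 4.3).
- One same-text label in the pool for conditions 10 and 11, none for the others (Table 2).
- Section 3: "FDA plans to allocate 2,080 to the control group and 480 to each treatment group at Session 1".
- Section 1: "estimated retention rates of between 50% - 100% for each follow-up session".

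**Step 1. Chance of being shown the same-text label.** With 3 labels drawn without replacement from 15, this is C(14,2)/C(15,3) = 91/455 = 0.20. For the other 14 conditions and for control it is 0.

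**Step 2. Participants affected.** With 50% retention at each of two follow-ups, Session 3 has 480 × 0.5 × 0.5 = 120 per treatment arm and 2,080 × 0.25 = 520 controls. With full retention it has 480 and 2,080. The same-text label is shown to 0.20 × 120 = 24 up to 0.20 × 480 = 96 participants per COPD arm.

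**Step 3. Size of the loss (assumed inputs).** Let *m* be the share who remember the statement and *g* the share of those with no usable memory of the image, who then guess between the two COPD labels and are wrong half the time. The loss in measured recall is 0.20 × *m* × *g* × 0.5.

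| *g* (assumed) | *m* = 0.6 | *m* = 0.8 |
|---|---|---|
| 0.05 | 0.3 points | 0.4 points |
| 1/3 | 2.0 points | 2.7 points |
| 1 | 6.0 points | 8.0 points |

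**Step 4. What this could do to a contrast (illustrative).** Assume true recall of 60% in control and 70% in a COPD arm. Measured recall in the COPD arm is 0.70 × (1 − 0.20 × *g* × 0.5). Power is for a two-sided test of two proportions at 0.05, before any FDR adjustment: Φ[(difference − 1.96 × *s*₀)/*s*₁], where *s*₀ is the pooled and *s*₁ the unpooled standard error.

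| *g* (assumed) | Measured recall | Power, 520 vs 120 | Power, 2,080 vs 480 |
|---|---|---|---|
| 0 | 70.0% | 53% | 99% |
| 0.05 | 69.65% | 50% | 98% |
| 0.5 | 66.5% | 26% | 76% |

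For example, with *g* = 0.5 and 520 vs 120, *s*₀ = 0.0493 and *s*₁ = 0.0481, so Φ[(0.065 − 0.0967)/0.0481] = 26%.

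The 20% is fixed by the design as written. Everything in steps 3 and 4 depends on *g*, which the SAP does not give.

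**The case against.** **Choosing the other COPD label is a genuine error.** E1 asks which label was seen, and the image is all that distinguishes conditions 10 and 11. This stands. A reader might infer that correct answers are being mis-scored, or that the recall estimate is biased for its stated target. The SAP does not support that, because it never defines the outcome as recall of the statement. What remains is unequal difficulty: the item demands memory of the image from one fifth of two arms and from nobody else.

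**Distractors overlap elsewhere too.** This also stands in part. Conditions 12 and 13 share reduced blood flow, 15 and 16 share blindness, and SG warnings 1 and 3 both mention pregnancy. Every control participant sees all four SG labels, so control recall may carry some confusion of its own, and the net direction of all such effects in the contrast with control is not established. In those pairs, however, the full statement still separates the labels. Only the identical-text problem is specific to conditions 10 and 11.

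**The two COPD warnings are not ranked against the other GHWs.** Correct. A reader might infer that a comparison among GHWs is spoiled, but only contrasts with control are planned.

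**The loss may be trivial.** It may be. Participants see the label in two sessions, each time on a rotating pack and in an advertisement, so many may remember the image. The 8-point end requires that none of them do.

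**The survey instrument may already exclude the same-text label.** It is not available for this review, so that is possible. The SAP states a random draw with no exclusion, and an unstated one cannot be presumed.

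**Conclusion.** The point holds as a limited measurement inequality. As section 4.3 is written, 20% of participants in conditions 10 and 11 face a distractor with identical text, and no other participant does. Measured recall in these two arms is lower than it would be without that distractor. The reduction is unknown: from under 1 to about 8 percentage points if 60–80% remember the statement and between 5% and all of those must guess between the images. It affects 2 of 16 Phase 3 tests and leaves Phases 1 and 2 untouched. Because it works against a finding of better GHW recall, it cannot create a false advantage for these warnings over control. It is worth correcting because the correction is specific and nearly free.

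**What to change.** State in section 4.3 that the three distractors are drawn from GHWs with a different text statement: label 11 is not eligible for condition 10, and label 10 is not eligible for condition 11. That leaves 14 eligible labels for these two arms and brings the 20% to 0. The cost is one rule in the survey randomiser. The small loss is that the item no longer tests whether participants can tell the two COPD images apart.

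If fielding has begun, record the distractor set shown to each participant and prespecify a sensitivity analysis of the condition 10 and condition 11 contrasts that leaves out those shown the same-text label. Because the distractors are drawn at random, those who remain are a random subset of the arm: about 96 of 120 up to 384 of 480. The cost is about 20% fewer participants in these two arms for that analysis. Sample size, model and the other outcomes do not change.
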